7.3.3 Specimen Shipment

Biological specimens will not be shipped to an outside location for analysis, except for plaque samples. Specimens will be taken, by GO Health staff, to the principal investigator’s laboratory, [name] and processed or stored for future analysis. Plaque samples will be stored at -80°C for later bacterial microbiological analysis at the Microbiome core facility. Tissue samples will be stored at -80° C until use for RNA extraction and at 4°C for histological processing.

7.4 Questionnaire Administration

There are no questionnaires in place for this research study.

8 ASSESSMENT OF SAFETY

The principal investigator is responsible for all aspects of the conduct of the study. There will be a primary study coordinator assigned to track patients, IRB compliance, adverse events and protocol adherence and study deviations. The principal investigator will meet weekly with the study coordinator to track progress, enrollment and study adherence.

8.1 Specification of Safety Parameters

Safety monitoring reporting for this study will focus on unanticipated problems involving risks to participants, including unanticipated problems that meet the definition of a serious adverse event. Any adverse experience that is determined to be reportable to the Regulatory Authorities will be promptly reported to the Institutional Review Board (IRB).

8.1.1 Unanticipated Problems

The Office for Human Research Protections (OHRP) considers unanticipated problems involving risks to subjects or others to include, in general, any incident, experience, or outcome that meets **all** of the following criteria:

- unexpected in terms of nature, severity, or frequency given (a) the research procedures that are described in the protocol-related documents, such as the IRB-approved research protocol and informed consent document; and (b) the characteristics of the subject population being studied;
- related or possibly related to participation in the research (possibly related means there is a reasonable possibility that the incident, experience, or outcome may have been caused by the procedures involved in the research); and
- suggests that the research places subjects or others at a greater risk of harm (including physical, psychological, economic, or social harm) than was previously known or recognized.

8.1.2 Serious Adverse Events

A serious adverse event (SAE) is one that meets one or more of the following criteria:

- Results in death
- Is life-threatening (places the subject at immediate risk of death from the event as it occurred)
- Results in inpatient hospitalization or prolongation of existing hospitalization
- Results in a persistent or significant disability or incapacity
- Results in a congenital anomaly or birth defect

An important medical event that may not result in death, be life threatening, or require hospitalization may be considered an SAE when, based upon appropriate medical judgment, the event may jeopardize the subject and may require medical or surgical intervention to prevent one of the outcomes listed in this definition.

8.2 Reporting Procedures

The principal investigator will be responsible to monitor the overall study that includes the research data as well as the clinical procedures. All adverse events will be reported by the PI to the IRBs and appropriate agencies.

The Principal Investigator and study coordinator will review adverse events weekly and report them to the Institutional Review Board within 30 days. All “unanticipated” adverse events will be reported to the IRBs within 2 week of the investigator becoming aware of the event. Any related and unexpected serious adverse events (SAE) will be reported to the IRB within 24 hours of the principal investigator becoming aware of the event. Unanticipated patient deaths will be immediately reported to the IRB’s and NIH. A summarized copy of all adverse events will be submitted to the IRB’s annually or as requested.

Incidents or events that meet the Office of Human Research Protections (OHRP) criteria for **unanticipated problems** require the creation and completion of an unanticipated problem report form. OHRP recommends that investigators include the following information when reporting an adverse event, or any other incident, experience, or outcome as an unanticipated problem to the IRB:

- appropriate identifying information for the research protocol, such as the title, investigator’s name, and the IRB project number;
- a detailed description of the adverse event, incident, experience, or outcome;
- an explanation of the basis for determining that the adverse event, incident, experience, or outcome represents an unanticipated problem;
- a description of any changes to the protocol or other corrective actions that have been taken or are proposed in response to the unanticipated problem.

Adverse Event (AE)

An adverse event is any unfavorable and unintended diagnosis, sign (including an abnormal laboratory finding), symptom, or disease temporally associated with the study intervention, whether or not related to the intervention. Adverse events include new events not present during the pre-intervention period and pre-existing conditions that have increased in severity.

Expected clinical/dental Adverse Events (AE's)

- Aphthous and canker lesions
- Tooth sensitivity
- Cheek bite
- Linealba
- Gingival soreness
- Mild gingival inflammation
- Mild gingival bleeding
- Mild tooth mobility
- Mild gingival abrasion or irritation
- TMJ pain and soreness

Unexpected Adverse Event

An unexpected adverse event is an adverse reaction, the nature or severity of which is not consistent with the clinical course of a subject receiving the study procedures. Expected events are untoward clinical occurrences that are perceived by the investigator to occur with reasonable frequency in the aforementioned study procedures. Examples of adverse events that are expected include aphthous and canker lesions, tooth sensitivity, cheek bite, linealba, gingival soreness, mild gingival inflammation, mild gingival bleeding, mild tooth mobility, mild gingival abrasion or irritation, and TMJ pain and soreness. Such events, will not be considered reportable unless the event is considered by the investigator to be unexpectedly severe or frequent for an individual patient. If expectedness of an event is unclear, the study's Principal Investigator will be consulted to make this determination.

Serious Adverse Event (SAE)

A serious adverse event is any untoward medical occurrence that meets the definition of adverse event and results in death, is life-threatening, requires or prolongs hospitalization, causes persistent or significant disability/incapacity, results in congenital anomalies/birth defects or, in the opinion of the investigators, represents other significant hazards or potentially serious harm to research participants or others.

Grading of Adverse Events

The following scale will be used to grade the severity of adverse events noted during the study:

Severity Criteria:

- 1 = Mild adverse event – Did not interfere with normal activity
- 2 = Moderate adverse event – Interfered with normal activity to some extent
- 3 = Severe adverse event – incapacitating with inability to work or do usual activity

Serious Criteria:

- 1 = Caused or prolonged hospitalization
- 2 = Resulted in persistent or significant disability/incapacity
- 3 = Congenital anomaly/birth defect
- 4 = Life threatening
- 5 = Fatal
- 6 = Other event considered serious by investigator. Site investigators may use their discretion in classifying events as serious if they represent a significant hazard or potentially serious harm to research participants or others.

Attribution of Adverse Events

Site investigators will also evaluate the association of each AE with the periodontal intervention according to the following categories:

- a. Unrelated: Adverse event(s) clearly not be related to investigational procedure(s)/agent(s) or other intervention.
- b. Unlikely: Adverse event(s) doubtfully related to investigational procedure(s)/agent(s) or other intervention.
- c. Possibly: Adverse events(s) may be related to investigational procedure(s)/agent(s) or other intervention; known to occur but the temporal relationship is unclear; other causes are possible or biologically very plausible.
- d. Probably: Adverse event(s) likely associated with investigational procedure(s)/agent(s) or other intervention; known to occur and temporal relationship is appropriate or improvement is seen upon withdrawal of study drug; other causes are unlikely.
- e. Definitely: Adverse event(s) clearly associated with the investigational procedure(s)/agent(s) or other intervention; known to occur and clear temporal relationship is noted or improvement is seen upon withdrawal of study drug; other causes are very unlikely. If re-challenge is attempted, the adverse event must return.

*An adverse event will be considered associated with the study procedures if in the estimation of the local investigator the event is at least possibly related to the study procedures.

Reporting Adverse Events

All AEs and SAEs will be recorded on the electronic AE Eorm incorporated in the CDART “Dental Toolkit” Module. Adverse events that are (1) unexpected, (2) related or possibly related to participation in the research, and (3) serious or suggest that there are new or increased risk(s) to subjects or others is promptly reportable to UNC Office

of Human Research Ethics (OHRE) within 7 calendar days of the investigator becoming aware of the information. The Principal Investigator will assure that documentation of each event is adequate to permit accurate inferences regarding causation (e.g., temporal associations, onset, course, response to patient or physician intervention, alternative etiologies) and severity.

All unanticipated problems will be reported to **NIDCR's centralized reporting system** via Rho Product Safety:

- Product Safety Fax Line (US): [name]
- Product Safety Fax Line (International): [contact]
- Product Safety Email: [contact]

General questions about SAE reporting can be directed to the Rho Product Safety Help Line (available 8:00AM – 5:00PM Eastern Time):

- US: [name]
International: [contact]

9 STUDY OVERSIGHT

The investigator will be responsible for study oversight, including monitoring safety and ensuring that the study is conducted according to the protocol and ensuring data integrity. The principal investigator will review the data for safety concerns and data trends at regular intervals, and will promptly report to the IRB and NIDCR any Unanticipated Problem (UP), protocol deviation, or any other significant event that arises during the conduct of the study.

10 CLINICAL SITE MONITORING

Clinical site monitoring will not be done for this study; however, the NIDCR reserves the right to conduct independent audits or clinical monitoring as necessary.

11 STATISTICAL CONSIDERATIONS

11.1 Study Hypotheses

The central hypothesis of this proposal is that IFI16 functions to attenuate the host response that drives periodontitis. We propose to investigate whether macrophage-derived IFI16 expression modulates tissue inflammation via AIM2. Human tissues will be used for confirming results generated by the principal investigator from in vitro and in vivo models that show high expression of AIM2 and IFI16 under inflammatory conditions (4). Better characterization of the cellular and molecular biology of inflammasomes will help identify important potential therapeutic targets for the treatment and prevention of periodontal diseases. The following “hypothesis” corresponding to Study Objective 1 (section 3.1) is:

Primary hypotheses corresponding to the second study objective **will be tested**:

- 1a. There will be a temporal change in expression of AIM2 (mRNA fold change and percentage of positive cells for histological analysis) induced by SIBO in healthy and severe periodontitis subjects
- 1b. There will be a temporal change in expression of IFI16 (mRNA fold change and percentage of cells for histological analysis) induced by SIBO in healthy and severe periodontitis subjects
- 1c. There will be differences in temporal changes in expression of AIM2 (mRNA fold change and percentage of cells for histological analysis) induced by SIBO between healthy and severe periodontitis subjects
- 1d. There will be differences in temporal changes in expression of IFI16 (mRNA fold change and percentage of cells for histological analysis) induced by SIBO between healthy and severe periodontitis subjects

Exploratory hypotheses corresponding to the second study objective will be assessed:

- 2a. The stent-induced change in expression of protein AIM2 will correlate with differentially expressed (between healthy and severe periodontitis subjects) periodontal pathogens identified by 16S rDNA (% of total reads) at baseline (visit 2)
- 2b. The stent-induced change in expression of protein IFI16 will correlate with differentially expressed (between healthy and severe periodontitis subjects) periodontal pathogens identified by 16S rDNA (% of total reads) at baseline (visit 2)
- 2c. The stent-induced change in expression of protein AIM2 will correlate with the temporal change in periodontal pathogens identified by 16S rDNA (% of total reads)
- 2d. The stent-induced change in expression of protein IFI16 will correlate with the temporal change in periodontal pathogens identified by 16S rDNA (% of total reads)

11.2 Sample Size Considerations

In order to evaluate the expression of IFI16 and AIM2 in subjects, 72 (36 subjects/group) will be recruited from the patients, students, staff and general population at the University of North Carolina-School of Dentistry. We will enroll 72 subjects to accommodate a 10% drop-out rate. Individuals with healthy tissues and severe periodontitis will be enrolled based on Morelli et al 2017 (1). Sample size calculations are based, in part, on preliminary cross-sectional (non-SIBO experiment) data on expression levels of Aim2 from immunohistochemistry reported in Xue et al. (2015; Table 3) who reported statistically significant differences in healthy (n=10; mean=0.50; s.d.=0.14) and severe periodontitis (n=10; 0.97; s.d.=0.27) subjects with respect to AIM2 expression from immunohistochemical analyses. For the first study objective (section 3.1), there will be 99% power to detect differences in AIM2 and IFI16 expressions at Visit 2 between healthy and severe periodontitis at these levels using two-sided t-tests at the 0.05 significance level. When comparing change in AIM2 expression levels from visit 2 to visit 5, assumptions of a common standard deviation of 0.25 and an intra-subject correlation of 0.40 across the two time points indicate that power will be at least 80% to determine differences in change between healthy and severe periodontitis subjects that are as small as 0.40; in a worst case (but not realistic) scenario, an intra-subject correlation of 0 would give 80% power to detect differences in temporal change that are as small as 0.50. Xue et al (2015; Figure 1c) found no statistically significant cross-sectional differences between healthy and severe periodontitis subjects with respect to mRNA expression of AIM2; they did not report this data numerically precluding power analysis.

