Gingival Tissue/Biopsy: Biopsy samples of gingival tissues will be collected from all individuals at baseline and 21-days of biofilm-overgrowth. A trained dentist will use a scalpel blade to collect 2 biopsy samples per subject for a total of 128 samples. Samples will be obtained using topical and local anesthesia. Each biopsy shall be ≤ 0.5 cm thick. Biopsies will only be collected from the papillae of posterior teeth. The scalpel blade shall be oriented in an inverse bevel direction to capture the base of the periodontal pocket or gingival sulcus. Each biopsy will contain oral epithelium, gingival connective tissues and loosely adherent cells lining the periodontal pocket. Papillae height will be retained by using vertical mattress suture technique, minimizing facial reduction, and coronal reposition of the flap. The biopsy wound will be undermined with minimal flap reflection and closed with a suture. Post-operative instructions, including placing ice over the surgical area and avoiding hot liquids for the remainder of the day, will be given to the subject.

Gingival biopsy samples will be bi-sectioned for immunohistochemistry/immunofluorescence imaging and mRNA expression.

1. For **RNA** extraction, samples will be immediately placed in RNeasy[®] (Ambion Inc.) which is an aqueous, non-toxic tissue storage reagent that rapidly permeates tissue to stabilize and protect cellular RNA *in situ* in unfrozen specimens. Samples will be placed in a microfuge tube containing ~1ml of RNeasy and kept at 4°C overnight, then RNeasy is removed. Samples will be stored at -80°C until used for analysis.
2. For **Immunohistochemistry/Immunofluorescence**, samples will be fixed in 4% paraformaldehyde and stored at -20°C for 24 hours and then placed in 70% ethanol for further analysis.

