Using 16s rRNA sequencing, expression counts for a large number (~20,000) of Operational Taxonomic Units (OTUs) with known taxonomy will be obtained from 72 samples at baseline and among them approximately 64 samples at Day 21 of SIBO. A few hundred taxa will be identified by collapsing expression data within genera corresponding to candidate periodontal pathogens. Change in pathogen levels from baseline to Day 21 among severe periodontitis subjects will be assessed with univariate Wilcoxon Signed Rank tests applied to each OTU (hypothesis 2f) or Wilcoxon Rank Sum Tests for comparison of Day 21 minus baseline differences in expression counts between healthy and severe periodontitis groups (hypothesis 2h). False discovery rate (FDR; Benjamini and Hochberg, 1995) and family-wise error rate (FWER; Hochberg, 1988) methods, e.g., as described in Preisser et al. (2011), will be applied to resulting *p*-values for exploratory and confirmatory testing, respectively, to identify statistically significant taxa.

Temporal changes in periodontal pathogen levels that are statistically significant controlling for multiple testing as described above will be correlated with stent-induced changes in AIM2 and IFI16 proteins using Spearman rank correlation coefficients and corresponding 95% confidence intervals.

Statistical computation for analysis of the data will be done by [name] in consultation with [name] and [name].

All hypothesis tests that are observed to be NOT statistically significant will be reported as being inconclusive.

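### Section 11.2: the 80% detectable differences in AIM2 change (0.40 and 0.50) are about twice what the stated SD of 0.25 and about 32 evaluable per group give (about 0.20 and 0.25)

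*Combined protocol and SAP*

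**What the plan says.** Section 11.2 plans 36 subjects per group: "We will enroll 72 subjects to accommodate a 10% drop-out rate". For the between-group comparison of AIM2 change it makes "assumptions of a common standard deviation of 0.25 and an intra-subject correlation of 0.40 across the two time points" and concludes that "power will be at least 80% to determine differences in change between healthy and severe periodontitis subjects that are as small as 0.40". It adds that a correlation of 0, described as an unrealistic worst case, would give "80% power to detect differences in temporal change that are as small as 0.50".

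For the cross-sectional comparison, by t-test (two-sided, 0.05), it says "there will be 99% power to detect differences in AIM2 and IFI16 expressions at Visit 2 between healthy and severe periodontitis at these levels". The levels are those of a cited pilot study of AIM2 by immunohistochemistry: healthy mean 0.50, SD 0.14; severe periodontitis mean 0.97, SD 0.27; 10 subjects in each group. For AIM2 mRNA, it says of the pilot authors that "they did not report this data numerically precluding power analysis".

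Two other sections fix the evaluable number. Section 7.3.1 has the dentist "collect 2 biopsy samples per subject for a total of 128 samples", and section 11.3 expects "72 samples at baseline and among them approximately 64 samples at Day 21 of SIBO" for the plaque analysis.

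**The concern.** An SD of 0.25 per visit with about 32 subjects per group should detect a difference in change well below 0.40. The printed limits looked too large for the stated inputs, which means that an input or a result in the paragraph is wrong.

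These are the plan's only figures for what the between-group comparison of AIM2 change by histology (hypothesis 1c in section 11.1) can detect. Section 11.3 will report every non-significant test as inconclusive. To interpret such a result, a reader needs to know whether the trial had 80% power near 0.2 or only near 0.4 to 0.5, and the text as printed does not settle that.

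**Working it through.** **Inputs**

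- SD at each visit 0.25; correlation 0.40, worst case 0 (section 11.2).
- Evaluable n: 36 × 0.9 = 32.4 per group (11.2); 128 biopsies / 2 = 64 subjects (7.3.1); about 64 Day 21 samples (11.3). All point to 32 per group.
- Two-sided 0.05 t-test. Section 11.2 states this for Visit 2; it is assumed here for change. Section 11.3 plans a Wilcoxon rank sum test at 0.05 for change, so that test is checked as well.

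**Attempt to reproduce 0.40 and 0.50**

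SD of change = 0.25 × √(2(1 − ρ)):

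- ρ = 0.40: 0.25 × √1.2 = 0.274
- ρ = 0: 0.25 × √2 = 0.354

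Standard error of the difference in mean change = SD of change × √(2/32):

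- ρ = 0.40: 0.0685
- ρ = 0: 0.0884

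With 62 degrees of freedom, the noncentral t distribution gives 80% power when the difference is 2.846 standard errors:

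| | ρ = 0.40 | ρ = 0 |
|---|---|---|
| Printed in 11.2 | 0.40 | 0.50 |
| t-test, 32 per group | 0.195 | 0.252 |
| Printed / computed | 2.05 | 1.99 |
| t-test, 36 per group | 0.183 | 0.237 |
| Rank sum, 32 per group (efficiency 3/π, normal data) | 0.20 | 0.26 |
| Power at the printed value, t-test, 32 per group | 99.99% | 99.98% |

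A rank sum simulation with normal data and 20,000 replicates gave 79.6% power at 0.20 (ρ = 0.40) and 80.3% at 0.26 (ρ = 0), in line with the table.

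**Variants that keep SD 0.25 and 32 per group**

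- 99% power instead of 80%: 0.298 and 0.385.
- Alpha of 0.05/8 = 0.00625: 0.252 and 0.326.
- Correlation of −1, the most extreme value possible: SD of change 0.50, detectable difference 0.356.

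None reaches 0.40 and 0.50.

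**Departures from the stated inputs that do come close**

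| Reading | 80% detectable, ρ = 0.40 | 80% detectable, ρ = 0 | Power at 0.40 (ρ = 0.40) | Power at 0.50 (ρ = 0) | Visit 2 power |
|---|---|---|---|---|---|
| SD 0.25, 9 per group | 0.385 | 0.497 | 82.8% | 80.4% | 99.1% |
| SD 0.50, 32 per group | 0.390 | 0.503 | 82.0% | 79.5% | >99.99% |

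Visit 2 power uses a difference of 0.97 − 0.50 = 0.47 and the pilot SDs, pooled as √((0.14² + 0.27²)/2) = 0.215. It does not depend on the SD assumed for change.

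The 9-per-group reading comes closest to all three printed figures, but no section gives that n. The SD 0.50 reading keeps the planned n. Since 0.50² = 0.25, a variance may have been printed as an SD. However, 0.50 is 1.85 times the larger pilot SD (0.27), and this reading does not explain the printed 99%.

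**The case against.** The strongest reply is that nothing printed overstates the trial's sensitivity. With SD 0.25 and 32 per group, power of at least 80% at 0.40 is literally true. If an SD of 0.50 was meant, the printed differences are about right and only the SD needs changing. On either reading no test, significance level or enrolment figure moves, so the point could be called minor.

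Much of this stands: the error is conservative if SD 0.25 holds, and there is no case here that the trial is underpowered for this comparison. It does not rescue the text. Both sentences present their figure as the smallest difference detectable, and the 0.50 sentence states 80% power outright where the inputs give 99.98%. Nor can a reader tell which correction applies.

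A second reply is that the 9-per-group reading is only a guess. Its match to the 99% depends on an equal-variance t-test with the pilot SDs; a Welch test gives 98.8% by simulation, and the common SD of 0.25 gives 96.2%. The 99% may also be just a rounded floor. That is fair. The reading is worth checking but is not established.

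A third reply is that the histology measure does have a unit, since section 11.1 names a percentage of positive cells. That is so, but 11.2 does not say how 0.25, 0.40 and 0.50 relate to that percentage.

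**Conclusion.** The concern holds. The 80% detectable differences of 0.40 and 0.50 do not follow from SD 0.25 and about 32 evaluable subjects per group. Those inputs give 0.195 and 0.252 by t-test, or about 0.20 and 0.26 by the planned rank sum test. The printed values are too large by a factor of about 2.

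This assumes equal SDs at both visits and in both groups, equal evaluable numbers, and a two-sided 0.05 level for change; the rank sum figures also assume normality. The documents do not show whether the n, the SD or the results are wrong. The conclusion covers AIM2 by immunohistochemistry only: section 11.2 supplies no IFI16 data and says that mRNA power could not be calculated.

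**What to change.** Retrieve the original calculation and state in 11.2 the n per group, the SD, the test and the measurement unit used. Check first whether about 9 per group was entered. Then make one of two corrections.

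If SD 0.25 and 32 per group are right, replace the statement on change with, for example:

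> For AIM2 by immunohistochemistry, with 32 evaluable subjects per group, a common SD of 0.25 at each visit and a two-sided 0.05 rank sum test (normality assumed), power is 80% for a between-group difference in change of about 0.20 at an intra-subject correlation of 0.40, or about 0.26 at a correlation of 0.

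If an SD near 0.50 was intended, correct the 0.25 and justify the larger value against the pilot SDs of 0.14 and 0.27.

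In either case, give the Visit 2 t-test power separately as above 99.9% at the pilot means and SDs, and either limit that sentence to AIM2 or add the IFI16 data behind it. Do not extend the corrected figures to mRNA or IFI16.

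The cost is rewording a few lines of 11.2. Enrolment, tests and procedures stay as they are.
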